**Medtronic Business Restricted**

**CONFIDENTIAL**

056-F275 Rev E Clinical Investigation Plan Template

## 18. Version History

Version	Summary of changes	Author(s)/Title
1.0	

Version 1.0, 03/JAN/2020 initial revision for updated 522 order of 10/JAN/2020

	Avenu Medical
1.1	

Version 1.1, 25/FEB/2020 update per interactive review discussion on 14/FEB/2020

	Avenu Medical
1.2	

Version 1.2, 23/MAR/2020 update per new 522 order on 10/JAN/2020

	Avenu Medical
1.3	

Version 1.3 final, 23/APR/2020

	

**Medtronic Business Restricted**

**CONFIDENTIAL**

056-F275 Rev E Clinical Investigation Plan Template

# Ellipsys Vascular Access System Post Market Surveillance Study Clinical Investigation Plan

MDT20052

Version 4.0

Page 62 of 64

Medtronic

2.0	

• CIP transferred into MDT 056-F275 template

• Study Sponsor updated from Avenu Medical to Medtronic Vascular Inc.

• Primary and Secondary Endpoints updated; Ancillary Endpoints added

• Definition of Newly Trained Provider added

• Inclusion Criteria updated to remove requirement for urine/blood pregnancy test

• Exclusion Criteria added to exclude patients with an active COVID-19 infection or relevant history of COVID-19

• Unscheduled Visit removed as a follow-up visit type

• Reportable adverse events limited to only those adverse events related to the device, procedure, or secondary procedures, and any serious adverse events (including SAEs, ADEs, SADEs, and UADEs)

	[name], Principal Clinical Research Specialist
-----	---	---

**Medtronic Business Restricted**

**CONFIDENTIAL**

056-F275 Rev E Clinical Investigation Plan Template

# Ellipsys Vascular Access System Post Market Surveillance Study Clinical Investigation Plan

MDT20052

Version 4.0

Page 63 of 64

Medtronic

3.0	

• CIP transferred to version D of MDT 056-F275 template

• Sponsor address updated

• General Inclusion Criterion 7 updated to include Allen's Test

• General Exclusion Criterion 13 updated

• Number of allowable sites increased to up to 14

• Maximum number of subjects allowable per site increased to 27

• Section 9.11 added to define Secondary Procedures

• Throughout document Removed 'UADE' from site reportable adverse events

• Section 11.4 Updated Table 6 of to 'Intra- procedure (index) PTA balloon angioplasty or planned PTA/balloon maturation procedure' and added definition note for 'planned PTA/balloon maturation procedure'

• Section 11.4 Table 6 Added 'Cannulation'

	[name], Senior Principal Clinical Research Specialist
4.0	

• CIP transferred to version E of MDT 056-F275 template

• All references to Secondary Procedure CRF have been updated to Adjunctive/Secondary Procedure CRF

• Section 2, updated to correct a numbering error

• Section 2, safety assessment section updated to correct incorrect reference section

• Section 9.1, table 1 footnote 2 updated to clarify when the

	[name], Senior Clinical Research Specialist

**Medtronic Business Restricted**

**CONFIDENTIAL**

056-F275 Rev E Clinical Investigation Plan Template

# Ellipsys Vascular Access System Post Market Surveillance Study Clinical Investigation Plan

MDT20052

Version 4.0

Page 64 of 64

Medtronic

	
determination of secondary procedures begins
 

• Section 9.8 updated to add 'If a complication or adverse event occurs intra-procedure, the details should be captured in the Adverse Event CRF ' and 'If any secondary procedures are required to mature or maintain the AVF or re-establish flow subsequent to completion of the AVF procedure, they will be documented in the Adjunctive/Secondary Procedure CRF and the AE CRF if applicable. '

• Sections 9.8 and 9.11 updated to add instructions for procedures done during the AVF creation.

• Section 9.11 updated to further clarify definition of secondary procedures

• Section 9.11 updated to include reminder to complete AE CRF if the secondary procedure is done because of an adverse event

• Section 9.15 Deleted unanticipated and (UADE) for consistency

• Section 11.1 updated for consistency to indicate Adverse events are collected from the point of enrollment through study exit

• Section 13.3.1 updated to clarify definition of secondary procedure

• Section 13.3.3 updated to clarify definition of secondary procedure

• Section 17 moved before section 18 to correct numbering order

	
--	---	--

**Medtronic Business Restricted**

**CONFIDENTIAL**

056-F275 Rev E Clinical Investigation Plan Template

2. List of Abbreviations and Definitions of Terms

Abbreviation	Definition
AE	Adverse Event
AVF	Arteriovenous (AV) Fistula
CEC	Clinical Events Committee
CI	Confidence Interval
CVC	Central Venous Catheter
EDC	Electronic Data Capture
HD	Hemodialysis
PS	Post-market Surveillance
PTA	Percutaneous Transluminal Angioplasty
SAE	Serious Adverse Event
SAP	Statistical Analysis Plan
SD	Standard Deviation
VAQ	Vascular Access Questionnaire

3. Introduction

This document outlines the detailed statistical methods to be implemented for the data collected within the scope of the Ellipsys Vascular Access System Post Market Surveillance Study. This Statistical Analysis Plan (SAP) has been designed to document, before data are analyzed, the rationale for the study design, and the planned analyses that will be included in study reports. The purpose of this plan is to provide a framework within which answers to the study objectives can be achieved in a statistically rigorous fashion, without bias or analytical deficiencies.

Specifically, the plan has the following purpose: To prospectively outline the types of analyses and presentations of data that will form the basis for conclusions to be reached that will answer the study objectives outlined in the protocol, and to explain in detail how the data will be handled and analyzed, adhering to commonly accepted standards and practices of statistical analysis in the medical device industry.

4. Study Objectives

The primary objectives of this post-market surveillance study are to support short-term safety of the device and procedure and further assess long-term safety and effectiveness in subjects treated by newly trained providers of the Ellipsys Vascular Access System in the creation of a native AV fistula (AVF) via percutaneous access in subjects who are on hemodialysis and are medically indicated for the creation of an upper limb anastomosis.

4.1 Primary Objectives

The primary objectives will assess safety and effectiveness in subjects by measuring the early occlusion rate, the long-term serious adverse event (SAE) rate and cumulative patency.

4.1.1 Primary Endpoints

To evaluate the Ellipsys Vascular Access System, this study design shall include three primary endpoints; two based on the safety of the device during treatment and post-operative outcomes and one based on the effectiveness performance of the device. The primary endpoints are as follows:

Primary Safety Endpoints

Early occlusion:

Early occlusion defined as the percentage of subjects with a total occlusion within 7 days of the AVF creation procedure.

Study related serious adverse events through 12 months:

Rate of serious adverse events through 12 months related to the device, study procedure or secondary procedure to maintain or reestablish patency.

An independent clinical events committee (CEC) will assess and adjudicate any potential relationship to the device and/or procedures per the criteria set in the CEC charter.

Primary Effectiveness Endpoint

Cumulative patency through 12 months post-AVF creation:

Cumulative patency is defined as freedom from access abandonment from time of access creation.

4.2 Secondary Objectives

Secondary objectives include descriptive analyses of secondary endpoints as well as acute procedural observations and clinical utility measures. There are no formal hypothesis tests or sample size requirements for the secondary objectives.

4.2.1 Secondary Endpoints

The following secondary endpoints to be evaluated in this study are as follows:

1. Primary patency through 12 months post-AVF creation:

Defined as freedom from access thrombosis or any intervention designed to facilitate, maintain or reestablish patency measured from time of access creation through 12 months.

2. Assisted primary patency through 12 months post-AVF creation:
Defined as freedom from access thrombosis from time of access creation through 12 months.
3. Secondary procedure Rate:
Defined as the percentage of subjects having one or more surgical or percutaneous interventions designed to mature or maintain the AVF or re-establish flow. Secondary procedures are procedures subsequent to completion of the AVF creation procedure. This endpoint will also be summarized by type of procedure, indication, procedure success and association with any adverse events (AEs).
4. Overall patient safety:
A full characterization of all adverse events during the study.

4.3 Ancillary Objectives

Ancillary objectives include descriptive analyses of ancillary endpoints as well as acute procedural observations and clinical utility measures.

4.3.1 Ancillary Endpoints

The following ancillary endpoints to be evaluated in this study are as follows:

1. Functional Patency Rate Through 12 months: *Defined as freedom from access abandonment from the time of first two-needle cannulation.*
2. Physiological Maturation Rate at 3, 6, and 12 months: *Defined as the percentage of access sites with access vessel minimum blood flow rate $\geq 500\text{mL/min}$ and minimum diameter $\geq 5\text{mm}$ as measured by duplex ultrasound.*
3. Functional Cannulation Success Through 12 months: *Defined as the time to achieve successful use of the endovascular AVF, with two-needle access and at least two hours of dialysis through the access, for more than two-thirds of the dialysis sessions over a continuous 28-day period after access creation.*
4. Days of Central Venous Catheter (CVC) Exposure through 12 months
5. Subject Satisfaction using the Vascular Access Questionnaire (VAQ) at 6 months
6. Nurse-Cannulator Satisfaction at 3, 6, and 12 months
Subjective and objective parameters will be assessed including fistula characteristics, cannulator training, skills and experience cannulating this type of fistula.

5. Investigation Plan

This study is a prospective, non-randomized, multi-center, single-arm, observational, post-market surveillance (PS) study of the Ellipsys Vascular Access System. The study will be conducted by newly trained providers in subjects on hemodialysis and medically indicated for creation of an upper limb anastomosis. Subjects will be followed for 12 months (+2 month window) following the AVF creation procedure.

6. Determination of Sample Size

The sample size is not driven by a statistical hypothesis. To ensure that a minimum of 100 subjects will be evaluable at the 12-month follow-up visit, a minimum of 134 subjects will be enrolled in the study. This sample size estimate allows for a 25% drop-out rate ($100/.75 = 134$ subjects) which may result due to a higher than normal attrition rate seen in this study population due to the natural history of the disease state. Newly trained users from up to 14 sites in the United States will participate in the study. Each study site will enroll no more than 20% of the total enrollment (134 subjects), with a maximum of 27 subjects.

7. Statistical Methods

7.1 Study Subjects

7.1.1 Disposition of Subjects

A STROBE flow diagram will be used to describe the disposition of study subjects for analysis of the primary objectives.

Ellipsys Vascular Access System Post Market Surveillance Study Statistical Analysis Plan

Revision 2.0

Page 7 of 25

Form

Medtronic

Figure 1 shows an example of a blank STROBE flow diagram. Subject enrollment status will be presented for all enrolled subjects, followed by number of subjects with a procedure attempt, number of subjects with successful access creation and follow-up compliance thereafter. Subject enrollment will also be presented for each site as the number of subjects enrolled, number with procedure attempts, and number with access created.

An access failure occurs when the Ellipsys device is not deployed due to access failure defined as 1) the needle or wire cannot be introduced, or 2) vessel spasm precludes continuing the procedure. Subjects with an access failure may be re-scheduled for another attempt at access or followed through discharge and exited. If the second access attempt is also not successful, these subjects will be considered access failures and followed for safety through clinic discharge. If the second access attempt is more than 30 days after the initial screening, the subject will be re-screened and given a new subject identification number; the new number will be linked to the previous subject identification number in Electronic Data Capture (EDC) to prevent subjects being included twice in the analysis.

Subject visit compliance, and end of study status will be presented for enrolled subjects in whom the procedure has been attempted and the Ellipsys Vascular Access System deployed, whether successful or not. For each study visit, the following information will be tallied: in window visits, out of window visits, early terminations, deaths, and missed visits. Overall follow-up compliance will be reported as number of subjects who had a follow-up visit within or out of window divided by total number of eligible subjects. The number and percentage of subjects who did/did not complete the study will be summarized overall as well as for each reason for withdrawal or early termination.

Follow-up:

Study exit might include the following reasons:

- Study completed
- Subject lost to follow-up
- Subject death
- Subject did not meet inclusion/exclusion criteria
- Subject was not treated with the study device
- Subject did not provide consent
- Subject chooses to withdraw (e.g., consent withdrawal, relocation to another geographic location)
- Investigator deems withdrawal necessary (e.g. medically justified, inclusion/exclusion criteria not met, failure of subject to maintain adequate study compliance)

[figure not shown]
Analysis:

Analysis can only be completed for subjects that have case report forms saved complete.

Allocation:

Since the Ellipsys post-market surveillance study is not a randomized study, all study subjects that are enrolled are allocated to the intervention (i.e. are treated with the Ellipsys Vascular Access System).

Figure 1 – Example of STROBE Flow Diagram

7.1.2 Clinical Investigation Plan (CIP) Deviations

Protocol deviations will be summarized as the number of events as well as the number and percentage of subjects.

Deviations may include, but are not limited to the following:

- Failure to obtain informed consent prior to participation
- Incorrect version of the informed consent form used
- Failure to obtain IRB approval before the start of enrolling subjects in the study
- Included subject did not meet inclusion/exclusion criteria
- Required testing and/or measurements not done or incorrectly done
- Subject did not attend follow-up visit
- Follow-up visit was completed outside window
- Unauthorized use of Ellipsys system outside of CIP
- Adverse events/Unanticipated Adverse Device Effects (UADE) or device deficiencies not reported in the required timeframe as specified in the CIP
- Source data permanently lost
- Enrollment of subjects during lapse of IRB approval
- Enrollment limits exceeded

7.1.3 Analysis Sets

The study populations are defined as follows:

- The **Safety population** is defined as all enrolled subjects in whom the procedure has been attempted and the Ellipsys Vascular Access System deployed, whether successful or not.

The Safety Population may include device failures. A device failure is defined as a malfunction of the Ellipsys Vascular Access System during use that precludes creation of a percutaneous AV fistula. A second Catheter may be deployed or a second Controller may be used to complete the procedure.

The Safety population may include procedure failures. A procedure failure is when the Ellipsys Vascular Access System is deployed and functions per specification, however, the AV fistula creation is unsuccessful due to incorrect placement in the patient anatomy. If this is observed immediately after deployment and the introducer sheath or guidewire is still in place, a second deployment may be attempted to complete the procedure.

- The **Treated population** is defined as all subjects in the Safety population with AVF successfully created.

Summaries of baseline parameters will be based on the Safety population. Summaries of the primary safety analyses will be based on the Safety population. Primary effectiveness and secondary endpoint analyses will be based on the Safety and/or Treated population, as indicated in the following sections. In the event a subject has more than one AVF access attempt, the first attempt will be used in summaries and analyses of the Safety population, and the final attempt will be used in summaries and analyses of the Treated population.

7.2 General Methodology

For continuous variables, the number of observations, mean, standard deviation (SD), median, minimum, and maximum will be calculated, unless otherwise stated. For categorical variables, frequencies and percentages will be calculated. Exact binomial confidence limits will be calculated based on Wilson-score methods.

Survival analysis will also be performed for time-to-event endpoints using the Kaplan-Meier method. In cases where adjustment for competing risks is necessary, cumulative incidence curves will also be provided.

To assess the continued safety of the AVF creation procedure post-market, a subset of study endpoints will be descriptively compared to the pre-market study (DEN170004) results where possible. Comparisons will be performed using the Safety population for each study.

7.3 Handling of Missing, Unused, and Spurious Data and Dropouts

For all study endpoints that use time-to-event analysis as the primary analysis, patients lost to follow-up or who have died will be treated as censored or as a competing risk for observation of the endpoint. In instances where partial dates are provided, information from the partial date and other dates provided for the patient will be used to determine a plausible range of possible dates, and then the midpoint of that range will be used.

Missing data for primary safety objective #1 may result from a study procedure attempted but not completed, or loss to follow-up or death prior to endpoint assessment. Missing data for secondary and ancillary endpoints may result from clinical assessments unable to be performed due to a remote visit, or unanswered questions on the Subject and Cannulator Satisfaction surveys. Additionally, not all ultrasound measurements of artery and vein diameters and mean flow rates will be available due to normal variations in subject anatomy. These missing values will be excluded from summaries and analyses. In general, imputation of missing data will not be performed for descriptive statistics.

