7.7.6 Ancillary Objective #2

Physiological Maturation Rate at 3-, 6-, and 12-months

Analysis Dataset:

Treated Analysis Set per section **Error! Reference source not found..**

Analysis Method:

Physiological maturation will be summarized at each relevant follow-up visit as the number and percentage of subjects achieving the endpoint along with exact two-sided 95% confidence limits for the percentage, calculated via the Wilson method. The endpoint will be summarized separately at 3, 6 and 12 months.

Endpoint Definition:

Physiological maturation is defined in an access site as access vessel minimum blood flow rate $\geq 500\text{mL/min}$ and minimum diameter $\geq 5\text{mm}$ as measured by duplex ultrasound.

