10.2 Additional Analysis

The following additional analyses may be performed.

1. *Characterization of adjunctive procedures*

Analysis Dataset:

Safety Analysis Set per section **Error! Reference source not found..**

Analysis Method:

Adjunctive procedures will be summarized as a listing. The type of procedure (e.g. banding, coils, stents, etc.), indication (due to stenosis, due to AE, etc.), procedure success and association with any AEs will be provided.

Endpoint Definition:

Adjunctive procedures are defined as any additional procedure that occurred during the AVF creation procedure. Balloon angioplasty during the AVF creation procedure is not considered an adjunctive procedure.

2. *Ultrasound measurements of artery and vein diameter and mean flow rate*

Analysis Dataset:

Treated Analysis Set per section **Error! Reference source not found..**

Analysis Method:

Ultrasound measurements of artery and vein diameters and mean flow rates will be summarized descriptively. Mean flow rate and diameter recorded at visits prior to identifying a well-defined target vessel will be summarized by vessel. Once a well-defined target vessel is identified, mean flow rate and diameter associated with the target vessel will be summarized both by vessel and in an aggregated manner.

Endpoint Definition:

Measurement of artery and vein diameter and flow rate by Duplex ultrasound.

2. *Target vessel location*

Analysis Dataset:

Treated Analysis Set per section **Error! Reference source not found..**

Analysis Method:

The number of subjects with each target vessel location at 3, 6, and 12 months shall be enumerated. Any changes in target vessel location during the study shall be noted.

3. *Investigator assessments of arterial, venous, and AVF patency*

Analysis Dataset:

Treated Analysis Set per section **Error! Reference source not found..**

Analysis Method:

The number of subjects with confirmed patency at each visit shall be enumerated.

4. Hemodialysis access

Analysis Dataset:

Treated Analysis Set per section **Error! Reference source not found..**

Analysis Method:

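### Physiological maturation can be overstated: SAP 7.3 drops missing ultrasound values, and SAP 7.7.6 sets no denominator or rule for failed accesses that were not scanned

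*SAP*

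**What the plan says.** The endpoint requires a minimum flow of at least 500 mL/min and a minimum diameter of at least 5 mm in the access vessel, by duplex ultrasound. SAP 7.7.6 uses the Treated population and states: "Physiological maturation will be summarized at each relevant follow-up visit as the number and percentage of subjects achieving the endpoint". It names the interval method ("exact two-sided 95% confidence limits for the percentage, calculated via the Wilson method") but not the denominator at a visit. The unit also differs between sections: SAP 4.3.1 words the endpoint as "Defined as the percentage of access sites with access vessel minimum blood flow rate", while 7.7.6 counts subjects.

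The missing-data rule is in SAP 7.3. It foresees that "not all ultrasound measurements of artery and vein diameters and mean flow rates will be available due to normal variations in subject anatomy". For secondary and ancillary endpoints more broadly it says: "Missing data for secondary and ancillary endpoints may result from clinical assessments unable to be performed due to a remote visit". It then states "These missing values will be excluded from summaries and analyses" and adds "In general, imputation of missing data will not be performed for descriptive statistics". Protocol 13.1 carries the same exclusion. Neither section mentions an abandoned or occluded access as a reason for a missing value.

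Other sections bear on this:

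- The Treated population (SAP 7.1.3) is every Safety-population subject whose fistula was created, so it keeps fistulas that fail later.
- Protocol section 9 follows these subjects for 12 months. Table 1 and section 9.10 call for ultrasound at every follow-up visit. Abandonment is not among the exit reasons in 9.16.1.
- SAP 10.2 lists last-known statuses that include abandonment before first function, abandonment after it, and a fistula working again after occlusion and intervention.
- SAP 7.8.1 writes out the denominator for early occlusion, and SAP 7.7.1 says how transplant-related abandonment is handled for cumulative patency. Maturation has no counterpart to either.

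**The concern.** Exclusion is reasonable when a value is missing for reasons unrelated to the outcome, such as anatomy or a remote visit. It is not neutral when failure of the access is itself the reason for having no value. A subject whose fistula has been abandoned may have no access-vessel flow or diameter to record, yet is known not to have a mature access. If that subject is dropped, the numerator stays the same and the denominator shrinks.

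The reported figure then describes maturation among accesses that could be measured, while reading as maturation among created fistulas. Because abandonment accumulates, the distortion could be larger at 12 months than at 3 months, and a flat reported rate could hide a falling one.

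**Working it through.** **The plan's own figure.** The only related number is the enrollment target: 100 / (1 − 0.25) = 133.3, rounded up to 134. It reproduces. No maturation, abandonment or unscanned rate is given, so everything below is an assumed scenario.

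**Formula.** Let N be the Treated subjects in follow-up at the visit, a the failed accesses with no ultrasound value, and m the mature share among the N − a measured.

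- Failed and unscanned excluded: rate = m
- Failed and unscanned counted as not matured: rate = m × (N − a) / N
- Difference = m × a / N

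**Range.** With a/N from 5% to 20% and m from 60% to 90%, the smallest difference is 0.60 × 0.05 = 3 points and the largest is 0.90 × 0.20 = 18 points.

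**Whole-number illustration.** N = 100 (the plan's 12-month evaluable target), m about 75%, two-sided 95% Wilson intervals:

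| Abandoned, no scan | Excluded | Counted as not matured | Difference (points) |
|---|---|---|---|
| 5 | 71/95 = 74.7% (65.2–82.4) | 71/100 = 71.0% (61.5–79.0) | 3.7 |
| 10 | 68/90 = 75.6% (65.8–83.3) | 68/100 = 68.0% (58.3–76.3) | 7.6 |
| 15 | 64/85 = 75.3% (65.2–83.2) | 64/100 = 64.0% (54.2–72.7) | 11.3 |
| 20 | 60/80 = 75.0% (64.5–83.2) | 60/100 = 60.0% (50.2–69.1) | 15.0 |

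If the rows were successive visits, the reported rate would stay near 75% while the rate among all followed subjects fell from 71% to 60%.

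**Dependence on the unscanned share.** Take 15 failed accesses of 100, with 64 mature. The reported rate is 64 / (100 − number of failed accesses without a value):

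- none unscanned: 64/100 = 64.0%
- 4 unscanned: 64/96 = 66.7%
- 8 unscanned: 64/92 = 69.6%
- 11 unscanned: 64/89 = 71.9%
- all 15 unscanned: 64/85 = 75.3%

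The effect therefore runs from zero to 11.3 points on the same clinical outcomes.

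**The opposite error.** Suppose 10 of 100 values are missing for reasons unrelated to outcome and the true rate is 75%. Exclusion gives 67.5/90 = 75.0%. Scoring every missing value as failure gives 67.5/100 = 67.5%. A blanket missing-equals-failure rule would understate the rate, so the rule has to depend on the known status of the access.

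**The case against.** The plan never says that abandoned accesses are removed. SAP 7.3 excludes missing values, not named groups of subjects. Ultrasound is scheduled at every visit with no exemption for a failed access, and abandonment does not end follow-up. Since 7.7.6 names the Treated set and a percentage of subjects, a full Treated denominator is a possible reading. Abandonment is also the event in cumulative and functional patency and appears in the last-known status table, so failure is visible elsewhere. The endpoint is ancillary, has no formal test (Protocol 13.4), and is not one of the two pre-market comparisons anticipated in SAP 7.4.

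Much of this stands. It limits the point to a descriptive figure and makes the inflation a possibility rather than a certainty. It does not remove the gap: the exclusion rule is the only written instruction for a missing ultrasound value, and nothing in 7.7.6 overrides it when the access is known to have failed.

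Two stronger readings are tempting and are not supported:

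- A reader might infer that fistulas that never mature leave the denominator. A scanned fistula below either threshold is a measured non-success and stays in. SAP 10.2 expects measurements by vessel before a target vessel is settled, and only then "Once a well-defined target vessel is identified, mean flow rate and diameter associated with the target vessel will be summarized". A never-matured access could drop out only if no access-vessel value were recorded.
- A reader might infer that the rate will be inflated by a definite amount that grows over time. Both the size and the trend depend on how many failed accesses go unscanned, which the documents do not state.

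**Conclusion.** The point holds as a gap whose written default can favour the device. An abandoned or occluded access without a flow or diameter value can leave the maturation denominator although its outcome is known, and each one that leaves raises the reported rate. Under the stated assumptions (5% to 20% abandoned and all unscanned, 60% to 90% of measured accesses mature) the inflation is 3 to 18 points. If every failed access is scanned and scored, it is zero. None of these inputs comes from the documents. Early occlusion, study-related serious adverse events, cumulative patency and the sample size are unaffected. The change is worth making before analysis, because the percentage cannot be interpreted without knowing who is in its denominator.

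**What to change.** In SAP 7.7.6, with SAP 7.3 and Protocol 13.1 aligned, specify at each of 3, 6 and 12 months:

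1. Start from all Treated subjects alive and in the study at the visit, and use one unit (subjects or access sites) in both 4.3.1 and 7.7.6.
2. Count as not matured any access that is abandoned by the visit, or occluded at the visit, and has no qualifying ultrasound.
3. Score an access that was occluded and later reopened by its measurement at the visit.
4. Report abandonment due to kidney transplant separately, consistent with its handling in 7.7.1.
5. Exclude only missing scans of accesses that are patent or of unknown status, and report their number by reason.
6. Add a bounding analysis for unknown status: all counted as mature, then all as not mature.

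The cost is one rule and two aligned sentences. No new data are needed: abandonment is already required for the primary effectiveness endpoint, and investigator assessments of patency are summarized by visit in SAP 10.2. The downside for the sponsor is that the rate may be slightly less favourable.
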